7.3. Other Safety Analyses

The analyses of non-laboratory safety test results including ECGs and vital signs will be based on GSK Core Data Standards, unless otherwise specified. The details of the planned displays are presented in [Appendix 9: List of Data Displays](#).

Display Type	Absolute				Change from Baseline			
	Summary		Individual		Summary		Individual	
	T	F	F	L	T	F	F	L
Electrocardiograms (ECGs)								
ECG Findings	Y			Y [2]				
ECG Values				Y [3]				
Vital Signs								
Vital Signs	Y			Y [3]	Y			
Liver								
Liver Events [1]				Y				

NOTES :

1. Displays contain only participants with DAIDS toxicities for HIV-infected patients
2. Displays contain only participants with abnormal findings
3. Displays contain only participants with values of potential clinical importance
 - T = Table, F = Figure, L = Listing, Y = Yes display generated.
 - Summary = Represents TFL related to any summaries (i.e. descriptive statistics) of the observed raw data.
 - Individual = Represents TFL related to any displays of individual participant observed raw data.
 - Summary = Represents TFL related to any summaries (i.e. descriptive statistics) of the observed raw data.
 - Individual = Represents TFL related to any displays of individual participant observed raw data.

8. PHARMACOKINETIC ANALYSES

8.1. Primary Pharmacokinetic Analyses

8.1.1. Overview of Planned Pharmacokinetic Analyses

The PK analyses will be based on the PK Population, unless otherwise specified.

Table 3 provides an overview of the planned analyses, with full details being presented in [Appendix 9: List of Data Displays](#).

Table 3 Overview of Planned Pharmacokinetic Analyses

Endpoints	Untransformed				Loge-Transformed			
	Summary		Individual		Summary		Individual	
	F	T	F	L	F	T	F	L
Plasma Drug Concentrations	Y ^[1] [2]	Y	Y ^[1]	Y				
Derived PK Parameters	Y ^[3]	Y	Y ^[3]	Y		Y		

NOTES :

- T = Table, F = Figure, L = Listing, Y = Yes display generated.
- Summary = Represents TFL related to any summaries (descriptive statistics) of the observed raw data.
- Individual = Represents FL related to any displays of individual subject observed raw data.
- Tmax and tlag are not log transformed.

1. Linear and Semi-Log plots will be created on the same display.
2. Mean (+SD) and Median plots will be generated.
3. Individual and Box Plot of DTG and RPV PK Parameters by Treatment

8.1.2. Endpoint / Variables

8.1.2.1. Drug Concentration Measures

Refer to [Appendix 5: Data Display Standards & Handling Conventions \(Section 10.4.3 Reporting Standards for Pharmacokinetic\)](#)

8.1.2.2. Derived Pharmacokinetic Parameters

Pharmacokinetic parameters will be calculated by standard non-compartmental analysis according to current working practices and using the currently supported version of WinNonlin 6.3 or higher. All calculations of non-compartmental parameters will be based on actual sampling times. Pharmacokinetic parameters listed will be determined from the plasma concentration-time data, as data permits.

Parameter	Parameter Description
AUC(0-t)	Area under the concentration-time curve (AUC) from time 0 (predose) to time of the last quantifiable concentration, to be calculated using the linear trapezoidal rule for each incremental trapezoid and the log trapezoidal rule for each decremental trapezoid.
AUC(0-24)	Area under the concentration-time curve (AUC) over time 0 (predose) to 24 hours

Parameter	Parameter Description
	after dose administration, to be calculated using the linear trapezoidal rule for each incremental trapezoid and the log trapezoidal rule for each decremental trapezoid.
AUC(0-72)	Area under the concentration-time curve (AUC) over time 0 (predose) to 72 hours after dose administration, to be calculated using the linear trapezoidal rule for each incremental trapezoid and the log trapezoidal rule for each decremental trapezoid.
AUC(0-∞)	Area under the concentration-time curve from time 0 (predose) extrapolated to infinite time, calculated as: $AUC(0-\infty) = AUC(0-t) + Ct / \lambda z$ where Ct is the last observed quantifiable concentration.
%AUCex	The percentage of AUC(0-∞) obtained by extrapolation (%AUCex) will be calculated as: $[AUC(0-\infty) - AUC(0-t)] / AUC(0-\infty) \times 100$
Cmax	Maximum observed concentration, determined directly from the concentration-time data.
Ct	The last observed quantifiable concentration
C24	The observed concentration at 24 hours after dose administration
t	time of last quantifiable concentration
Tmax	Time to first occurrence of Cmax
Tlast	Time of last quantifiable concentration
tlag	Lag time before observation of drug concentrations in sampled matrix
t½	Terminal phase half-life will be calculated as: $t\frac{1}{2} = \ln 2 / \lambda z$
λz	Terminal-phase rate constant
CL/F	The apparent oral clearance
Vz/F	The apparent volume of distribution during the terminal phase

NOTES:

- Additional parameters may be included as required.

8.1.3. Population of Interest

The primary pharmacokinetic analyses will be based on the “Pharmacokinetic” population, unless otherwise specified.

8.1.4. Statistical Analyses / Methods

Details of the planned displays are provided in [Appendix 9: List of Data Displays](#) and will be based on GSK Data Standards and statistical principles.

Unless otherwise specified, endpoints / variables defined in Section [8.1.2](#) will be summarised using descriptive statistics, graphically presented (where appropriate) and listed.

For each of the Plasma DTG and RPV parameters $AUC_{(0-\infty)}$, $AUC_{(0-t)}$, C_{max} , t_{lag} , t_{max} , t , $t_{1/2}$, λ_z , $\%AUC_{ex}$, $AUC_{(0-24)}$, $AUC_{(0-72)}$, CL/F and Vz/F , C_t , and C_{24} , the following summary statistics will be calculated and tabulated by treatment (dose):

- **Untransformed Data :** N, n, arithmetic mean, %CV, 95% confidence interval (CI) for the arithmetic mean, SD, median, minimum, and maximum.
- **Loge-transformed Data:** Geometric mean, 95% CI for the geometric mean, SD of loge-transformed data and %CVb

For $\%AUC_{ex}$, T_{max} , t_{lag} , λ_z , t and Vz/F , the summary statistics specified for untransformed data above will be generated.

PK data will be listed and may be presented in graphical format and will be summarized descriptively. All PK data will be stored in the Archives, GlaxoSmithKline R& D. Statistical analyses of the PK parameter data will be the responsibility of Clinical Statistics, GlaxoSmithKline or their designee.

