9.4. Statistical Analyses

Final analyses will be performed after the completion of the study and final dataset authorization.

Data will be listed and summarized according to GlaxoSmithKline reporting standards where applicable.

Unless stated otherwise, descriptive summaries for continuous variables will include n, mean, standard deviation (SD), median, minimum, maximum; whereas, n and percent will be used as summary statistics for categorical variable. Geometric mean with

associated 95% CI, and the between-subject coefficient of variance (CV) (%CVb) for the geometric mean will be included for PK variables, where applicable.

Baseline or pre-dose assessment is the last available assessment prior to time of the first dose unless it is specified otherwise. If there are multiple assessments collected on the same scheduled time, the average of these assessments will be used. For tabulated safety summaries, only the scheduled assessments will be included in the summary tables.

Version 9.4 or higher of the Statistical Analysis Software (SAS) system will be used to analyze data as well as to generate tables, listings, and figures.

Complete details will be documented in the Reporting and Analysis Plan (RAP).

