2.2. Study Objective(s) and Endpoint(s)

Objectives	Endpoints
Primary Objectives	Primary Endpoints

To evaluate the PK of DTG and RPV following a single oral dose of DTG/RPV 50 mg/25 mg FDC in healthy, adult Japanese participants.	
Plasma DTG and RPV AUC_(0-∞), AUC_(0-t), C_{max}, t_{lag}, t_{max}, t, t_{1/2}, λ_Z, %AUC_{ex}, AUC₍₀₋₂₄₎, AUC₍₀₋₇₂₎, CL/F and Vz/F, C_t, and C₂₄ following a single oral dose of DTG/RPV 50 mg/25 mg FDC in healthy adult Japanese participants.
Secondary Objectives	Secondary Endpoints

To evaluate the safety and tolerability of DTG/RPV FDC in healthy, adult Japanese participants.	
Safety and tolerability parameters, adverse event (AE) /serious adverse events (SAE), observed and change from baseline clinical laboratory values, and vital sign assessments.

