10.9.5. Pharmacokinetic Tables

Pharmacokinetic: Tables					
No.	Population	IDSL / Example Shell	Title	Programming Notes	Deliverable [Priority]
PK Concentration Data					
4.1.	PK	PKCT1	Summary of DTG Plasma Pharmacokinetic Concentration-Time Data by Treatment		SAC [1]
4.2.	PK	PKCT1	Summary of RPV Plasma Pharmacokinetic Concentration-Time Data by Treatment		SAC [1]
PK Derived Parameters					
4.3.	PK	PKPT1	Summary of Derived DTG Plasma Pharmacokinetic Parameters (Non-Transformed) by Treatment	Parameters with units	SAC [1]
4.4.	PK	PKPT3	Summary of Derived DTG Plasma Pharmacokinetic Parameters (Loge-transformed) by Treatment	Parameters with units	SAC [1]
4.5.	PK	PKPT1	Summary of Derived RPV Plasma Pharmacokinetic Parameters (Non-Transformed) by Treatment	Parameters with units	SAC [1]
4.6.	PK	PKPT3	Summary of Derived RPV Plasma Pharmacokinetic Parameters (Loge-transformed) by Treatment	Parameters with units	SAC [1]

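### Does the inconsistent wording on log-scale PK summaries in SAP 8.1.1 and 8.1.4 leave λz and Vz/F inadequately reported?

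*SAP*

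**What the plan says.** SAP 2.2 makes 15 plasma parameters per drug primary endpoints: AUC(0-∞), AUC(0-t), AUC(0-24), AUC(0-72), Cmax, Ct, C24, tlag, tmax, t, t1/2, λz, %AUCex, CL/F and Vz/F. Three statements in the SAP bear on the scale of their summaries.

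- SAP 8.1.4, opening list: all 15 receive the untransformed statistics (mean with CI, %CV, SD, median, range) and also the log-scale set, "Geometric mean, 95% CI for the geometric mean, SD of loge-transformed data and %CVb".
- SAP 8.1.4, following sentence: for %AUCex, Tmax, tlag, λz, t and Vz/F, "the summary statistics specified for untransformed data above will be generated".
- SAP 8.1.1, note to Table 3: "Tmax and tlag are not log transformed".

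Appendix 9 (SAP 10.9.5) plans a log-scale table for each drug, for example Table 4.4, "Summary of Derived DTG Plasma Pharmacokinetic Parameters (Loge-transformed) by Treatment". Its programming note does not say which parameters go in. Protocol 9.4 states that the geometric mean with "associated 95% CI, and the between-subject coefficient of variance (CV) (%CVb) for the geometric mean will be included for PK variables", but qualifies this as applying only where applicable and names no parameters.

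**The concern.** The three SAP statements do not match, and neither Appendix 9 nor the protocol settles the matter. Two programmers could each claim to follow the SAP and produce log-scale tables of different length for the primary endpoints. The opening list cannot be followed literally in all cases, since a tlag of 0 has no logarithm.

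Read as a restriction, the sentence on six parameters also splits linked quantities. SAP 8.1.2.2 gives the definition under "Terminal phase half-life will be calculated as" as ln2/λz, yet t1/2 would have a geometric mean and %CVb while λz would not. CL/F would have them and Vz/F would not. λz and Vz/F are positive, continuous quantities, for which geometric summaries are as natural as for t1/2 and CL/F.

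At stake would be the completeness of the primary PK tables, and a visible mismatch between the arithmetic means of λz and t1/2.

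**Working it through.** **1. Count the log-scale parameters under each statement.**

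| Statement | Taken off the log scale | Left on it |
|---|---|---|
| 8.1.4, opening list | none | 15 |
| 8.1.1, Table 3 note | Tmax, tlag | 15 − 2 = 13 |
| 8.1.4, next sentence as a limit | %AUCex, Tmax, tlag, λz, t, Vz/F | 15 − 6 = 9 |

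The nine are the four AUCs, Cmax, Ct, C24, t1/2 and CL/F.

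**2. Decide which statement governs.** The six parameters already have untransformed statistics from the opening list, so the next sentence adds nothing unless it means those statistics alone. A specific instruction of this kind normally overrides the general list before it. The Table 3 note names two of the same six and does not say that every other parameter is logged. It is incomplete, but it can stand beside the count of 9. The count of 13 arises only by inferring that whatever the note omits must be logged. The restrictive reading also avoids taking the log of a zero tlag.

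**3. What λz loses.** In each subject t1/2 = ln2/λz, so log λz = log(ln2) − log t1/2. Hence:

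- GM(λz) = ln2 / GM(t1/2);
- if the geometric CI for t1/2 is (L, U), that for λz is (ln2/U, ln2/L);
- the SD of the logs, and so %CVb, is the same for both.

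A check on one simulated sample of 13 gave GM(λz) = 0.016737 both directly and from t1/2, and %CVb = 33.1% for both. The t1/2 row already contains the whole log-scale summary of λz.

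**4. What Vz/F loses.** The SAP prints no formula for Vz/F. Assume the usual Vz/F = (CL/F)/λz, with the same subjects contributing. Then GM(Vz/F) = GM(CL/F) × GM(t1/2) / ln2. The same simulated sample gave 63.201 by both routes. The spread does not follow in the same way, because Var(log Vz/F) = Var(log CL/F) + Var(log t1/2) + 2 Cov(log CL/F, log t1/2), and the covariance is not tabulated. So the geometric CI and %CVb of Vz/F are absent from the tables. They can be computed from the individual values in Listings 32 and 33.

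**5. The mismatch of arithmetic means.** The documents give no CV for λz. Assume a lognormal distribution with CV 20%, 30% or 43.66%; the last is the upper bound that Protocol 9.2.1 gives for AUC and Cmax. Then AM(t1/2) × AM(λz) / ln2 = 1 + CV², and the half-life implied by the mean λz differs from the mean t1/2 by 1/(1 + CV²) − 1.

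| CV | 1 + CV² | Difference |
|---|---|---|
| 20% | 1.0400 | −3.8% |
| 30% | 1.0900 | −8.3% |
| 43.66% | 1.1906 | −16.0% |

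The arithmetic is right, but it does not measure an error in the plan. The SAP computes t1/2 subject by subject and summarises it directly on both scales. It nowhere back-calculates a half-life from the mean λz. Adding a geometric row for λz would also leave the mismatch where it is, because both arithmetic means would still appear in Tables 4.3 and 4.5.

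**The case for a change.** The strongest case for a change is about prespecification. The product of a descriptive study is its summary tables, and the SAP does not fix the content of two of them beyond argument. The sentence on six parameters lacks the word only, and the programming notes do not help. SAP 2.1 reports no departure from the protocol analysis, so an unexplained omission of geometric summaries for two suitable parameters sits awkwardly. One sentence listing parameters by scale would remove the doubt, with two more rows in each of Tables 4.4 and 4.6 and no new data.

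Some of this stands. The wording is inconsistent, and the geometric CI and %CVb of Vz/F are a real, if small, omission under the governing reading. The rest carries less weight.

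- The protocol's qualifier leaves room for the choice, so no protocol commitment is broken.
- The ambiguity and the loss cannot both be pressed in full. If 15 or 13 applied, λz and Vz/F would keep their geometric summaries. If 9 applies, the text is clear enough to follow.
- Of the two rows that would be added, the one for λz repeats t1/2.
- There is little room for choosing displays after seeing the data, because the doubtful rows are descriptive and no decision depends on them.

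SAP 10.4.3 also refers PK displays to the sponsor's display standards. These are not available here and may or may not fix the table content, so nothing above relies on them.

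**Conclusion.** This is a drafting slip that analysts can resolve sensibly from the text, and no change to the plan follows. On the natural reading, 9 of 15 parameters per drug get log-scale summaries. Taking tmax, tlag, t and %AUCex off that scale is sensible in any case. For λz nothing is lost. For Vz/F the only omission is the geometric CI and %CVb, while its untransformed mean with CI, %CV, SD, median and range are all reported.

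Followed as written, the single-arm study still gives sound results. SAP 2.4 states that no hypothesis is tested. The parameters that carry the PK description (AUC, Cmax, C24, CL/F and t1/2) have both scales whichever statement is followed. No conclusion would differ between the readings.

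This rests on reading the sentence about six parameters as a limit and, for Vz/F, on the usual relation to CL/F and λz in the same subjects. If the first assumption were wrong, λz and Vz/F would simply gain log-scale rows.

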10. APPENDICES

10.1. Appendix 1: Protocol Deviation Management and Definitions

Please refer to the Protocol Deviation Management Plan (PDMP).

10.1.1. Exclusions from PK Population

A subject meeting any of the following criteria will be excluded from the PK population:

Number	Exclusion Description
01	A subject with emesis occurring within 10 hours of the dose

10.2. Appendix 2: Schedule of Activities

10.2.1. Protocol Defined Schedule of Events

Procedure	Day -1	Study Intervention Period											Follow-Up (12 - 17 days post last dose) ^{2,3}	Notes			
		Day															
		1		2	3	4	6	8	10	12							
		Pre Dose	0 hr	Post Dose	24 hr	48 hr	~72 hr	~120 hr	~168 hr	~216 hr	~264 hr						
Admission to Unit	X																
Discharge					X												
Outpatient Visit						X	X	X	X	X	X						
Brief Physical Exam ¹	X																
Pregnancy test (urine or serum)	X										X						
Urine/Drug/Alcohol/Cotinine	X													Illicit Drug/Alcohol/Cotinine performed at the standard practice of the site.			
12-Lead ECG	X													Single ECGs will be collected			
Vital Signs (VS) measurements	X	X									X			Single VS measurements will be performed at all time points.			
Safety lab assessments (Hematology,Chemistry)	X					X								Glucose fasting is required approximately 10 hours prior to dosing on Day -1 and at least 6 hours at Day 3 post dose.			
DTG/RPV FDC Dosing			X											Subjects will fast for ~10 hours and receive the dose ~30 minutes (+ 5 minutes) after the start of a standardized moderate fat breakfast			

Procedure	Day - 1	Study Intervention Period										Follow-Up (12 - 17 days post last dose) ^{2,3}	Notes			
		Day														
		1		2	3	4	6	8	10	12						
		Pre Dose	0 hr	Post Dose	24 hr	48 hr	~72 hr	~120 hr	~168 hr	~216 hr	~264 hr					
Pharmacokinetic Sampling		X		Collected at 0.5, 1, 1.5, 2, 2.5, 3, 3.5, 4, 5, 6, 7, 8, 9, 12, 16, 24, and 48 hours post-dose			X	X	X	X	X		Subjects should be scheduled to provide PK samples in the morning on Days 4, 6, 8, 10, and 12; Days 8, 10, and 12 are for RPV sampling only. The 4-hour post-dose sample must be drawn prior to the subjects' first post-dose meal			
SAE Review	X	<=====X=====>										X				
AE Review		<=====X=====>										X				
Concomitant medication review	X	<=====X=====>										X				

10.3. Appendix 3: Study Phases

10.3.1. Study Phases

Assessments and events will be classified according to time of occurrence relative to the start and/or stop date of the study treatment.

Study Phase	Definition
Pre-Treatment	Date < Study Treatment Start Date
On-Treatment	Study Treatment Start Date ≤ Date ≤ Study Treatment Stop Date [+ 3 days]
Post-Treatment	Date > Study Treatment Stop Date [+ 3 days]

1. NOTES:

- If the study treatment stop date is missing then the assessment will be considered to be On-Treatment

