2.2. Background

TIVICAY (dolutegravir) was first approved in the United States in 2013 and is currently approved globally in more than 100 countries including, the Japanese Pharmaceuticals and Medical Devices Agency in 2014. DTG is an INI with low to moderate inter-subject PK variability, a predictable exposure-response relationship, and a 14-hour plasma half-life. Although co-administration of DTG with low-, moderate-, and high-fat meals increased DTG exposures (area under the plasma concentration-time curve from time 0 to infinity $AUC_{(0-\infty)}$ by 33%, 41%, and 66%, respectively), the TIVICAY product label states that the approved dose regimen is 50 mg once daily taken with or without food based on efficacy results of Phase 3 trials in treatment-naive or treatment-experienced, INI-naive patients who took DTG without regard to mealtimes [[TIVICAY USPI, 2015](#)]. More information on the efficacy, PK, safety and drug interaction potential of DTG based on an extensive program of Phase I to III clinical trials can be found in the Investigator Brochure (IB) [[GlaxoSmithKline Document Number RM2007/00683/09](#)].

EDURANT (rilpivirine), an NNRTI with *in vitro* activity against wild type virus and a broad range of NNRTI-resistant viruses, is approved in multiple countries including the US, Europe, Canada and Japan for the treatment of antiretroviral drug- naive patients (with viral load $\leq 100,000$ c/mL) at a dose of 25 mg once daily. RPV is primarily metabolized by CYP450 3A and has a half-life of approximately 50 h. The long half-life of RPV requires a lengthy PK sampling period of RPV to adequately characterize the terminal elimination phase and ensure that PK parameters are well-estimated. More

detailed information about efficacy, safety, and clinical pharmacology from an extensive program of Phase I-III clinical trials can be found in the RPV Investigator's Brochure [Janssen [EDMS](#) Number EDMS-ERI-3713711, 15.0., 2018].

JULUCA (dolutegravir and rilpivirine) is a fixed-dose single tablet containing a two-drug combination of dolutegravir and rilpivirine. JULUCA is indicated for the treatment of HIV-1 infection in ARV-experienced adult patients who are switching from their current ARV regimen to the 2-drug regimen while their viral load is suppressed to <50 copies/milliliter (c/mL). For more details, please reference the current JULUCA Prescribing Information [[Juluca USPI](#), 2017].

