8.3.1. Time Period and Frequency for Collecting AE and SAE Information

- All SAEs will be collected from the start of intervention until the follow-up visit at the time points specified in the [SoA](#). However, any SAEs assessed as related to study participation (e.g., study intervention, protocol-mandated procedures, invasive tests, or change in existing therapy) or related to a GSK product will be recorded from the time a participant consents to participate in the study.
- All AEs will be collected from the start of intervention until the follow-up visit at the time points specified in the [SoA](#).
- Medical occurrences that begin before the start of study intervention but after obtaining informed consent will be recorded on the Medical History/Current Medical Conditions section of the case report form (CRF) not the AE section.
- All SAEs will be recorded and reported to the sponsor or designee immediately and under no circumstance should this exceed 24 hours, as indicated in [Appendix 3](#). The investigator will submit any updated SAE data to the sponsor within 24 hours of it being available.
- Investigators are not obligated to actively seek AEs or SAEs after the conclusion of the study participation. However, if the investigator learns of any SAE,

including a death, at any time after a participant has been discharged from the study, and he/she considers the event to be reasonably related to the study intervention or study participation, the investigator must promptly notify the sponsor.

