2.3. Study Design

Design Features	
 This is a single dose, open-label study in adult Japanese healthy participants to evaluate the PK, safety and tolerability of DTG/RPV 50 mg/25 mg FDC tablets. The study will consist of screening, treatment and follow-up phases.
Dosing	
 Enrolled participants will receive the DTG/RPV 50 mg/25 mg FDC tablet as a single oral dose in a fed state.
Time & Events	
 Refer to Appendix 2: Schedule of Activities
Treatment Assignment	
 A maximum of 16 healthy adult Japanese subjects will be randomized such that a minimum of approximately 13 evaluable subjects complete the study with at least 3 participants of each gender enrolled.
Interim Analysis	
 There will be no interim analysis.

See study protocol for further details

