10.3.2. Study Phases for AE Data

Assessments and events will be classified according to time of occurrence relative to the start and/or stop date of the study treatment.

Study Phase	Definition
Pre-Treatment	Event Start Date < Initial Study Treatment Date
On-Treatment	If event onset date is on or after the initial treatment date & on or before the final treatment date with 3 days lag time. Initial Study Treatment Date ≤ Event Start Date ≤ Final Study Treatment Date + 3 days
Post-Treatment	If event onset date is after the final treatment date with 3 days lag time. Event Start Date > Final Study Treatment Date + 3 days
Onset Time Since 1 st Dose (Days)	If Treatment Date > Event Onset Date = Event Onset Date – Treatment Date If Treatment Date ≤ Event Onset Date = Event Onset Date – Treatment Date+1 Missing otherwise.
Duration (Days)	Event Resolution Date – Event Onset Date + 1
Drug-related	If relationship is marked 'YES' on eCRF OR value is missing.

NOTES:

- If the initial and final study treatment dates are missing then the event will be considered to be On-Treatment.

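### The SAP ends the on-treatment phase 3 days after the single dose, too short for rilpivirine, and its rule for missing AE stop days can put an event's end before its start

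*SAP*

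**What the plan says.** The study gives one dose. SAP 2.3 states: "Enrolled participants will receive the DTG/RPV 50 mg/25 mg FDC tablet as a single oral dose in a fed state".

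SAP 10.3.1 defines on-treatment for assessments as "Study Treatment Start Date ≤ Date ≤ Study Treatment Stop Date [+ 3 days". The brackets look like template text, but SAP 10.3.2 repeats the lag for AEs without them: "Initial Study Treatment Date ≤ Event Start Date ≤ Final Study Treatment Date + 3 days". An AE is post-treatment under this condition: "If event onset date is after the final treatment date with 3 days lag time". The SAP gives no reason for choosing 3 days. There is one fallback: "If the study treatment stop date is missing then the assessment will be considered to be On-Treatment".

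Protocol 2.2 gives DTG a plasma half-life of 14 hours. For the other component it says: "RPV is primarily metabolized by CYP450 3A and has a half-life of approximately 50 h". It adds that this long half-life is why PK sampling must be lengthy. Sampling runs to 264 h, and Days 8, 10 and 12 are for RPV only.

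On safety collection, protocol 8.3.1 says: "All AEs will be collected from the start of intervention until the follow-up visit at the time points specified in the" schedule of activities. Follow-up is 12 to 17 days after the dose, and a footnote to the schedule allows it on Day 12.

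SAP 10.6.2.1 covers AE dates with a missing day. A missing stop day becomes the last day of the month. If that falls after the treatment stop date, the treatment stop date is used instead. SAP 10.6.2.2 gives another rule for partial AE dates: a partial stop date goes to the end of the month, with December as the month, and no cap applies.

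**The concern.** The tablet contains two drugs with very different half-lives, and the 3-day lag suits only the shorter one. The protocol keeps measuring RPV, and keeps collecting AEs, on days that the SAP calls post-treatment. The secondary objective is the safety and tolerability of the combination. If an output or a narrative is split by this label, an event on Day 6 or Day 8 would be presented as arising after treatment while RPV may still be in the circulation.

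The label is not idle text. SAP 10.6.2.1 refers to the study-phase rule in connection with treatment-emergent AEs. Both imputation sections move ambiguous start dates towards on-treatment, and 10.6.2.2 calls this the worst case. A short lag works against that intent.

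The same reliance on treatment dates causes a second problem. In a single-dose study the treatment stop date is the dose date, so a cap at that date cannot work for an event that begins later.

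**Working it through.** The documents state no figure for this point, so there is none to reproduce.

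**Inputs**
- Doses: 1, so start date = stop date = Day 1 (SAP 2.3).
- Study day = date - first dose date + 1 (SAP 10.5.1).
- Lag: 3 days (SAP 10.3.1, 10.3.2).
- Half-lives: DTG 14 h, RPV about 50 h (protocol 2.2).
- Follow-up: 12 to 17 days after the dose (protocol 4.1), or Day 12 (footnote to the schedule of activities).
- AE duration = resolution date - onset date + 1 (SAP 10.3.2).

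**Step 1: end of the phase.** The last on-treatment date is dose date + 3, which is study Day 3 + 1 = 4.

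**Step 2: the lag in half-lives.** DTG: 72/14 = 5.14. RPV: 72/50 = 1.44. Five half-lives are 5 × 14 = 70 h (2.9 days) for DTG and 5 × 50 = 250 h (10.4 days) for RPV.

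**Step 3: fraction remaining,** taken as 0.5^(t/half-life), i.e. mono-exponential decline from the dose.
- DTG at 72 h: 0.5^5.14 = 2.8%.
- RPV at 72 h: 0.5^1.44 = 36.9%.
- RPV at 96 h, the latest that the Day 4 date could extend: 0.5^1.92 = 26.4%.
- RPV at 264 h, the last PK sample: 0.5^5.28 = 2.6%.

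**Step 4: share of the AE window labelled post-treatment** = (follow-up day - 4)/follow-up day.

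| Follow-up | Study day | Post-treatment dates | Share |
|---|---|---|---|
| Day 12 (footnote) | 12 | 8 of 12 | 66.7% |
| 12 days after dose | 13 | 9 of 13 | 69.2% |
| 17 days after dose | 18 | 14 of 18 | 77.8% |

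If on-treatment ran through the follow-up visit, the share would be 0 in every row.

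**Step 5: stop-date imputation under SAP 10.6.2.1.** Take an AE with a known start on study day d, later than Day 1, and a missing stop day. The last day of the stop month cannot precede the AE start, so it falls after the dose date. The cap therefore applies and sets the stop to Day 1. Duration = 1 - d + 1 = 2 - d.
- d = 2: 0 days.
- d = 3: -1 day.
- d = 6: 1 - 6 + 1 = -4 days.

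For any AE starting after the dose date, the imputed stop precedes the start. The duration is zero for a Day 2 start and negative from Day 3. With a cap at a Day 18 follow-up instead, the Day 6 event would last at most 18 - 6 + 1 = 13 days.

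**The case against.** The strongest reply is that no planned output is shown to use the phase label. Tables 3.1 to 3.3 and Listings 11 to 17 use the Safety population, and neither their titles nor their programming notes restrict them to on-treatment events. Protocol 9.4.2 says all safety data will be listed. Drug-relatedness follows the eCRF answer, with missing counted as related. Onset time since dose is derived separately. The reference in 10.6.2.1 to treatment-emergent AEs cites Appendix 4, whereas study phases are in Appendix 3, so it is thin evidence that phase drives reporting. All of this stands. A reader might infer that AEs after Day 4 will be dropped or under-counted, but the documents do not show that. The sponsor's display shells are not reproduced, so use of the label can be neither confirmed nor excluded.

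A reader might also infer that the lag damages the vital-sign endpoint, because the only scheduled post-dose reading is at follow-up. That follows from the schedule, and Tables 3.12 and 3.13 are not defined by phase, so the reading is summarised whatever its label.

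A lag of five RPV half-lives might seem enough. Rounded up to 11 days, it ends on Day 12 and still leaves 1 of 13 to 6 of 18 AE dates outside.

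On imputation, SAP 10.6.2.2 sends partial AE dates to data management first, and its own stop-date rule has no cap. The negative duration therefore arises only if the date stays partial and 10.6.2.1 is the rule programmed. That limits how often it can occur, but it leaves two rules that give different answers.

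**Conclusion.** The point holds as a classification problem and an imputation error. The on-treatment phase ends on Day 4, which is 5.1 DTG half-lives but 1.44 RPV half-lives, and 67% to 78% of the calendar days on which AEs are collected fall after it. That is a share of time, not of expected events. The RPV fraction of about 37% at 72 h rests on mono-exponential decline and on the half-life of approximately 50 h. The Day 4 limit assumes that the stop date is recorded as the dose date. If it is missing, the SAP classes the data as on-treatment.

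The effect on reported counts is conditional: none if phase is not used in programming, and a mislabelling of events during possible RPV exposure if it is. The stop-date cap in 10.6.2.1 does not depend on display choices. As written, it gives an impossible end date for any AE that starts after Day 1 and has a missing stop day. With at most 16 participants, few such records are likely, but each would carry a wrong duration.

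**What to change.** - In SAP 10.3.1 and 10.3.2, define on-treatment as from the dose through the follow-up visit, the collection window in protocol 8.3.1. Remove the bracketed lag.
- In SAP 10.6.2.1, cap an imputed AE stop date at the follow-up or study completion date, and never let it fall before the AE start date.
- Reconcile 10.6.2.1 with 10.6.2.2 so that one rule covers partial AE dates. State whether a recorded month is kept when only the day is missing, and correct the appendix reference.
- State whether any display is split or filtered by study phase.

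This is SAP wording and the matching derivation code, with no change to data collection. The downside is that a few late, unrelated events may be labelled on-treatment. The investigator's causality answer and the onset day remain available to distinguish them.
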